6.3.1.5. Minimal Disease Activity (MDA)

MDA is a measure to indicate disease remission, and is based on a composite score of 7 domains.

A subject will be classified as having achieved MDA when at least 5 out of 7 of the following criteria are met.

- TJC68 ≤ 1,
- SJC66 ≤ 1,

- $PASI \leq 1$ for subjects with a Baseline psoriasis covering at least 3% of the BSA (or for subjects with a Baseline psoriasis covering $BSA < 3\%$, this criterion is considered met),
- Patent’s Global Assessment of PsA pain intensity (PGAPI) score ≤ 15 (0 – 100 VAS),
- $PGADA \leq 20$ (0 – 100 VAS),
- $HAQ-DI \leq 0.5$,
- Leeds Enthesitis Index ≤ 1 for subjects with enthesitis at Baseline (or for subjects without enthesitis at Baseline, this criterion is considered met).

In the case that some of the MDA components are missing, the MDA assessment will be based on the nonmissing components. If nonmissing components are not sufficient to determine the MDA response, then the MDA response will be considered as missing.

6.3.1.6. FACIT-Fatigue

The FACIT-Fatigue scale is a brief, 13-item, symptom-specific questionnaire that specifically assesses the self-reported severity of fatigue and its impact upon daily activities and functioning in the past 7 days. The FACIT-Fatigue uses 0 (“not at all”) to 4 (“very much”) numeric rating scales. Negatively stated items are reversed by subtracting the response from “4” before being added to obtain a total score. Scores range from 0 to 52 with higher scores indicating less fatigue. In the case of missing response for some items in the questionnaire, if at least half of the items (i.e., ≥ 7 of 13 items) were answered at a given visit, the prorated score will be calculated and used in the analysis.

The FACIT-Fatigue scale and scoring guidelines are in [Appendix 2](#).

6.3.1.7. Dactylitis Assessments: Leeds Dactylitis Index (LDI)

LDI measures the ratio of the circumference of the affected digit to the circumference of the digit on the contralateral hand or foot using a Leeds Dactylometer.

LDI score is calculated as follows:

$$\text{LDI score of a dactylitic finger/toe} = \left\{ \left[\left(\frac{A}{B} \right) - 1 \right] \times 100 \right\} \times C$$

where

A = circumference of the dactylitic finger/toe (mm)

B = circumference of the contralateral digit (mm)

C = tenderness score (0 = no tenderness, 1 = tender)

If both ipsilateral and contralateral digits are thought to be dactylitic, then the reference range (given at the foot of the Dactylitis Score Sheet as in Protocol Appendix 25) will be used as the comparator (i.e., B in the above formula).

Binary tenderness score is used in LDI score calculation due to lack of reliability in the original Ritchie index. {Healy 2007}

Total LDI score equals to the sum of the non-negative individual LDI scores across all fingers and toes. Negative individual LDI scores will not be included in the total LDI score.

If there are missing fingers or toes, then the missing individual scores for those fingers or toes will not be included in the total LDI score. For subjects with dactylitis status absent for all the fingers and toes, their total LDI scores will be set as 0, and the tenderness score for each finger and toe will also be set as 0.

The summaries and analysis of LDI will be conducted on the FAS subjects with dactylitis at Baseline.

6.3.2. Analysis Methods for Key Secondary Efficacy Endpoints

For the superiority test of filgotinib 200 mg or filgotinib 100 mg group versus placebo control group in binary key secondary endpoints such as the ACR50 response rate at Week 12, the PASI75 response rate at Week 16 in subjects with psoriasis covering $\geq 3\%$ of the BSA at Baseline and the MDA response rate at Week 16, the observed response rate and 2-sided 95% CI based on normal approximation with continuity correction will be provided by visit. Non-stratified response rate difference along with its 95% CI calculated based on the normal approximation with continuity correction will be provided. Appendix 4 provides sample SAS models statements for constructing the confidence interval for the proportion. In addition, the p-value based on the logistic regression model same as the one used in section 6.2.2 with observed cases for testing the superiority of filgotinib 200 mg or filgotinib 100 mg as compared to placebo will be provided as well. In case of limited data leading to improper use of logistic model, the p-value will not be provided.

For non-inferiority test of filgotinib 200 mg or filgotinib 100 mg group versus adalimumab group in the ACR20 response rate at Week 12, the approach proposed by {Liu 2014} will be used to demonstrate that each filgotinib dose preserves more than 50% of the effect of adalimumab on the response rate of ACR20 at Week 12. Let π_T , π_C and π_P denote the true response rates of ACR20 for filgotinib, adalimumab and placebo, respectively, at Week 12, with corresponding variances σ_T^2 , σ_C^2 and σ_P^2 . The non-inferiority hypotheses are

$$H_{0,NI} : \frac{\pi_T - \pi_P}{\pi_C - \pi_P} \leq 0.5$$

vs

$$H_{1,NI} : \frac{\pi_T - \pi_P}{\pi_C - \pi_P} > 0.5$$

According to {Liu 2014}, the test statistics for non-inferiority (filgotinib preserves more than 50% of the effect of adalimumab) is

$$Z_{NI} = \frac{\hat{\pi}_T - 0.5\hat{\pi}_C - (1 - 0.5)\hat{\pi}_P}{\sqrt{\hat{\sigma}_T^2 + 0.5^2\hat{\sigma}_C^2 + (1 - 0.5)^2\hat{\sigma}_P^2}}$$

Note that the “hat” (^) denotes the estimated values of each parameter at Week 12. Missing data will be imputed using multiple imputation (MI) assuming that missing data are missing at random (MAR), which will follow the same method as described for the primary endpoint.

For the superiority test of filgotinib 200 mg or filgotinib 100 mg group versus placebo control group in continuous key secondary endpoints such as the change from baseline in HAQ-DI at Week 12, the change from Baseline in SF-36v2 PCS at Week 16, the change from Baseline in LEI at Week 16 for subjects with enthesitis at Baseline, the change from Baseline in FACIT-Fatigue at Week 16 and the change from Baseline in LDI at Week 16 for subjects with dactylitis at Baseline, a mixed-effect model repeated measures (MMRM) analysis that includes data at postbaseline visits through Week 16 will be applied. Subjects that have a baseline value and at least 1 postbaseline value are included in the analysis. The MMRM models will be used to evaluate treatment effect on change score from Baseline, with baseline value, stratification factors, treatment, visit, and treatment by visit interaction included as fixed effects and subject being the random effect. The MMRM model will include all treatment groups. An unstructured variance-covariance matrix will be used. The Kenward-Roger method will be used to estimate the degrees of freedom. Missing data will not be otherwise imputed using the MMRM approach. The least squares (LS) means and 95% CIs of the difference in mean change from Baseline between each filgotinib dose group and placebo group from MMRM will be provided at all the visits in Main study including Week 12 and Week 16.

In case of limited data leading to improper use of MMRM model, the descriptive statistics (sample size, mean, SD, median, Q1, Q3, minimum, and maximum) by treatment will be used for the continuous key secondary endpoints.

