1.3. Sample Size and Power

Sample size is determined based on the non-inferiority test of each filgotinib group compared to the adalimumab group on the ACR20 response rate at Week 12. When assuming the ACR20 response rate being 52% and 60% for the adalimumab and each filgotinib group, and 38.6% for the placebo group, 244 subjects in each filgotinib group and placebo group, and 122 subjects in the adalimumab group are required to obtain 90% power at a two-sided 0.025 significance level to demonstrate that filgotinib group preserves more than 50% of the effect of adalimumab with respect to the ACR20 response rate at Week 12.

A sample size of 244 subjects in each filgotinib group and the placebo group will provide over 95% power to detect a difference in ACR20 response rate of 21.4% at Week 12 (38.6% and 60% for the placebo group and each filgotinib group, respectively) using a two-sided 0.025 significance level superiority test.

In summary, the total sample size will be approximately 854 subjects per original planning.

The study was terminated per Sponsor’s decision after 67 subjects had been enrolled. At study termination, 13 out of 67 subjects continued on to the LTE, and 7 of those 13 subjects were terminated immediately after entering LTE phase. All the other subjects were prematurely discontinued from or completed the Main Study visits.

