6. EFFICACY ANALYSES

6.1. General Considerations

The primary analysis set for efficacy analyses will be the FAS, defined in Section 3.1.2.

Due to study early termination and insufficient number of subjects enrolled, all the hypothesis testings performed and p-values reported will be nominal, and, unless specified otherwise, all the confidence intervals will be calculated based on the nominal level of 95%. The results need to be interpreted with caution.

Efficacy analysis will be conducted on all available data during the Main Study phase (including data collected through the Week 16 visit after study drug discontinuation).

Estimands:

Treatment policy estimand is defined for the primary and key secondary as well as other secondary efficacy endpoints and will be the primary estimand for all the corresponding efficacy analyses:

- 1) Population: Subjects in the FAS.
- 2) Variable / endpoint: Primary and key secondary endpoints as well as other secondary endpoints (see details in subsequent Sections).
- 3) Strategy to address intercurrent events: include all on-study data regardless of protocol violations, use of rescue medication, change in background medication, and study drug discontinuation.
- 4) Population-level summary: treatment difference in the percentage of subjects meeting specific criteria for response defined by binary efficacy endpoints or mean treatment difference for continuous efficacy endpoints between each filgotinib group and placebo group or adalimumab group if applicable.

Selection of Efficacy Data in the Event of Multiple Records in an Analysis Visit Window

If multiple valid, nonmissing efficacy measurements exist in an analysis window, records will be chosen based on the following rules if a single value is needed:

- The record closest to the nominal day for that visit will be selected.
- If there are 2 records that are equidistant from the nominal day, or more than 1 record (with time known) on the selected day, the latest record will be taken.
- If chronological order cannot be determined (e.g., more than 1 record on the same day with time missing), for any given subject, the worst outcome will be selected.

Calculation of Composite Endpoints

For the calculation of composite endpoints including DAS28(CRP), ACR20/50/70, MDA, VLDA, PASDAS, DAPSA, PsARC, we use the following steps unless otherwise specified:

- Step 1: Assign individual components to analysis visit windows defined in Section 3.7.2

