6.2.2. Primary Analysis of the Primary Efficacy Endpoint

To test for superiority of filgotinib 200 mg or filgotinib 100 mg group versus placebo control group in proportion of subjects who achieve ACR20 at Week 12, a logistic regression analysis with treatment groups and stratification factors in the model will be used. The model will include all treatment groups. Missing data on the ACR20 response rate at Week 12 will be imputed using multiple imputation (MI) assuming missing at random (MAR):

- The MI procedure replaces each missing binary ACR20 value with a set of plausible values that represent the uncertainty about the right value to impute. Twenty imputed datasets will be generated with starting seed 12345. These multiple imputed data sets are then analyzed by using the same method for the primary analysis for complete data as specified above. The results from each set of imputed data sets will then be combined using Rubin’s rule {[Rubin 1987](#)}. The stratification factors and treatment groups will be included in the imputation model as covariates and all available data at post-baseline visits up to Week 16 visit will be included in the longitudinal model.

The p-value from the logistic regression model with MI for testing the superiority of filgotinib 200 mg or filgotinib 100 mg as compared to placebo will be provided. The 2-sided 95% confidence interval (CI) of the ACR20 response rate at Week 12 based on MI method will be provided for each treatment group. In addition, treatment difference in ACR20 response rate at Week 12 between each filgotinib dose group and placebo group along with its 95% CI calculated based on MI method will be provided.

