6.4.2. Analysis Methods for Other Secondary Endpoints

The FAS will be used for all summaries and analyses of other secondary efficacy endpoints.

For the binary endpoints of the ACR20 response, the ACR50 response, the PASI75 response in subjects with psoriasis covering $\geq 3\%$ of the BSA at Baseline and the MDA response, for subjects with observed outcome, the similar analysis as the key secondary endpoint analyses described in Section 6.3.2 will be applied. The proportions of subjects achieving above endpoints (observed case) will be plotted over time during Main study by treatment and by visit.

For all the other binary endpoints, only above mentioned observed response rate, 2-sided 95% CI and non-stratified response rate difference along with its 95% CI will be provided by visit.

For all the continuous endpoints, absolute value and change from Baseline will be summarized using descriptive statistics (sample size, mean, SD, median, Q1, Q3, minimum, and maximum) by treatment and by visit.

For the continuous endpoints of the change from baseline in HAQ-DI, the change from Baseline in SF-36v2 PCS, the change from Baseline in LEI for subjects with enthesitis at Baseline, the change from Baseline in FACIT-Fatigue and the change from Baseline in LDI for subjects with dactylitis at Baseline, plots of mean \pm SD for change from baseline by visit will be presented.

For time to event analyses, Kaplan-Meier plot of each treatment group during Main study will be provided. Number of subjects having events and censored, KM estimates of median (95% CI), Q1, Q3, minimum and maximum of the time to events will be summarized by treatment group.

The by-subject listing of each endpoint and corresponding components, if available, including data during the Main Study and LTE phases will be provided.

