Appendix 4. Sample SAS Code for Analysis of Binary Endpoints

The following model statement will be used to construct the confidence interval for the binomial proportion difference described in Section 6.3.2:

```
proc freq data = test ;  
  by avisitn;  
  tables TRT01PN*aval_ / riskdiff (CORRECT);  
  output out = f200vp_ci RISKDIFF;  
  where TRT01PN = 1 | TRT01PN = 3;  
run;
```

where the confidence interval for the difference of two independent binomial proportions is constructed based on the normal approximation (ie, the Wald method) with a continuity correction, to adjust for the difference between the normal approximation and the binomial distribution, which is a discrete distribution:

$$(\hat{p}_1 - \hat{p}_2) \pm \left(\frac{1}{2} \left(\frac{1}{n_1} + \frac{1}{n_2} \right) + z_{\alpha/2} \times \sqrt{\frac{\hat{p}_1(1 - \hat{p}_1)}{n_1} + \frac{\hat{p}_2(1 - \hat{p}_2)}{n_2}} \right)$$

The following model statement will be used to construct the confidence interval for the binomial proportion described in the Section 6.3.2:

```
proc freq data = test ;  
  by avisitn TRT01PN;  
  tables aval_ / BINOMIAL (CORRECT);  
run;
```

the confidence interval for the binomial proportions is constructed based on the normal approximation to the binomial distribution with continuity correction:

$$\hat{p}_1 \pm \left(\frac{1}{2} \left(\frac{1}{n_1} \right) + z_{\alpha/2} \times \sqrt{\frac{\hat{p}_1(1 - \hat{p}_1)}{n_1}} \right)$$

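### With roughly 10 to 19 subjects per arm, the SAP's continuity-corrected Wald 95% interval for a response rate collapses when an arm has no responders or all responders

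*SAP*

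**What the plan says.** SAP 6.3.2 covers ACR50 at Week 12, PASI75 at Week 16 and MDA at Week 16. For each arm, "the observed response rate and 2-sided 95% CI based on normal approximation with continuity correction will be provided by visit". For comparisons, "Non-stratified response rate difference along with its 95% CI calculated based on the normal approximation with continuity correction will be provided". Appendix 4 supplies the SAS code and both formulas; the single-rate interval "is constructed based on the normal approximation to the binomial distribution with continuity correction".

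SAP 6.4.2 applies a similar analysis to ACR20, ACR50, PASI75 and MDA at the other visits, and then restricts the rest: "For all the other binary endpoints, only above mentioned observed response rate, 2-sided 95% CI and non-stratified response rate difference" with its interval are to be given. That group includes VLDA, ACR70, PASI90, PASI100 and the remission endpoints.

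SAP 6.1 sets the level: unless specified otherwise, "all the confidence intervals will be calculated based on the nominal level of 95" percent. SAP 1.3 records that the study was stopped "after 67 subjects had been enrolled".

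The small-data provision for binary endpoints concerns the model p-value only: "In case of limited data leading to improper use of logistic model, the p-value will not be provided". No section gives another interval for an arm with 0 or n responders. For the primary endpoint, SAP 6.2.2 says that the 95% interval "of the ACR20 response rate at Week 12 based on MI method will be provided for each treatment group", so that analysis does not use the Appendix 4 formula.

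**The concern.** A Wald interval takes its width from the estimated variance, which is zero when nobody or everybody responds. What is then printed as a 95% interval is just 1/(2n), a quantity that does not depend on the confidence level. This SAP was written after enrolment had ended at 67, so sparse cells were foreseeable. Arms are small, the observed-case rule and the restriction of the PASI endpoints to those with at least 3% body surface involvement can only reduce n, and several endpoints are stringent and tabulated at early visits.

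For most of the binary endpoints this interval is the only measure of uncertainty attached to the rate. For ACR20, ACR50, PASI75 and MDA, an arm with no responders can make the logistic model unusable. The p-value is then dropped in the same cells where the interval is worst. A table row of 0/19 would seem to rule out any true rate above 2.6%.

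**Working it through.** **Inputs.** 67 enrolled (SAP 1.3); allocation 2:2:1:2 (SAP 1.2); the Appendix 4 formulas with z = 1.96; ACR20 planning rates of 38.6%, 52% and 60% (SAP 1.3). The documents give no actual arm counts and no expected rates for the stringent endpoints, so the low rates used below are assumptions.

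**The plan's own figure.** The SAP prints no numerical interval to reproduce. The nearest stated figure is the 90% power of the non-inferiority test in SAP 1.3. The effect is 0.60 − 0.5×0.52 − 0.5×0.386 = 0.147. The standard error is sqrt(0.24/244 + 0.25×0.2496/122 + 0.25×0.2370/244) = 0.0417. Power = Φ(0.147/0.0417 − 2.241) = 90.06%, which agrees. Total size 3×244 + 122 = 854 also agrees.

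**Arm sizes.** 67 × (2, 2, 1, 2)/7 = 19.1, 19.1, 9.6, 19.1, taken as 19, 19, 10, 19.

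**Single rate.** The formula is p̂ ± [1/(2n) + 1.96·sqrt(p̂(1−p̂)/n)]. At p̂ = 0 the half-width is 1/(2n); for n = 19 that is 1/38 = 2.6%. As written, 0/19 gives −2.6% to +2.6%. The table cuts limits at 0 and 100%, which the SAP does not state.

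| Responders | SAP | Exact (Clopper-Pearson) | Wilson |
|---|---|---|---|
| 0/19 | 0–2.6% | 0–17.6% | 0–16.8% |
| 19/19 | 97.4–100% | 82.4–100% | 83.2–100% |
| 0/10 | 0–5.0% | 0–30.8% | 0–27.8% |
| 0/5 (illustrative skin subset) | 0–10% | 0–52.2% | 0–43.4% |

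**Coverage of the single-rate interval, by full binomial enumeration.** Once the true rate exceeds 1/(2n), every sample with no responders misses it. At n = 19 and a true 3%, the chance of no responders is 0.97^19 = 56%, so coverage cannot exceed 44%.

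| n | True rate | Chance of no responders | SAP coverage | Wilson coverage |
|---|---|---|---|---|
| 19 | 2% | 68% | 100% | 95% |
| 19 | 3% | 56% | 44% | 98% |
| 19 | 5% | 38% | 62% | 93% |
| 19 | 10% | 13.5% | 86% | 96% |
| 19 | 15% | 4.6% | 95% | 95% |
| 10 | 5% | 60% | 100% | 91% |
| 10 | 10% | 35% | 65% | 93% |
| 10 | 15% | 20% | 80% | 95% |
| 10 | 20% | 11% | 89% | 97% |

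At the documents' own ACR20 rates the SAP interval covers 94.3% (n=19, 38.6%), 96.5% (n=19, 60%) and 94.3% (n=10, 52%). Over true rates of 30 to 60% it runs from about 88% to 97% across the two sample sizes.

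**Difference.** The half-width is ½(1/n₁ + 1/n₂) + 1.96·sqrt(p̂₁(1−p̂₁)/n₁ + p̂₂(1−p̂₂)/n₂). For 0/19 v 0/19 it is ½(2/19) = 5.3 points; Newcombe gives 16.8 points. Coverage at 19 v 19:

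| True rates | SAP coverage |
|---|---|
| 60% v 38.6% | 96.8% (mean width 0.71; Newcombe 95.0%, width 0.56) |
| 30% v 10% | 97.7% |
| 10% v 10% | 98.9% |
| 5% v 5% | 99.8% |
| 15% v 5% | 96.9% |
| 10% v 2% | 90.6% |
| 7% v 1% | 79% |

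**The case against.** The best case for leaving the text alone is that little depends on it. SAP 3.4, 6.1 and 6.5 make all testing nominal and ask for cautious reading, the primary analysis uses another interval, and the low rates that expose the fault are assumed. At the only rates the documents state, coverage is fine. That limits the consequence, and it is why this is not a critical point. It does not repair the interval: a general caution does not tell a reader that a 95% label may mean 44 to 65% coverage. The planning rates are for ACR20 and say nothing about ACR70, VLDA or PASI100.

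A second argument is that difference intervals are mostly conservative, so changing them is a matter of taste. This is largely true: equal rare rates, and several unequal pairs, cover above 95%. Under-coverage appears for some unequal rare pairs, as at 10% v 2% and 7% v 1%. Elsewhere the gain is a shorter interval.

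Third, the tables show counts, the untruncated lower limit is negative and so signals trouble, and SAP 6.4.2 adds Kaplan-Meier summaries and listings. The counts do let an alert reader notice. The Kaplan-Meier intervals concern time to low disease activity, a different quantity from the response rate at a visit.

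**Conclusion.** The concern holds. As specified, the interval labelled 95% has a half-width of 1/(2n) at 0 or n responders, and no section of the SAP provides an alternative. At 0/19 the upper limit is about one seventh of the exact one (2.6% against 17.6%). At n=19, coverage falls to 44% at a true rate of 3% and reaches the nominal level again at about 15%; at n=10 it is still 89% at 20%. By symmetry the same applies near 100%.

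The size rests on two assumptions: that the 2:2:1:2 ratio held among the 67 enrolled, and that some endpoints or visits have true rates in the low range shown. Smaller observed-case counts would widen the exact interval further. The collapse at 0 or n responders is a property of the formula and needs neither assumption. The change should be made, but no confirmatory conclusion depends on it.

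**What to change.** In SAP 6.3.2, 6.4.2 and Appendix 4, specify Wilson or Clopper-Pearson intervals for single response rates, and unstratified Newcombe or Miettinen-Nurminen intervals for the differences. In the Appendix 4 PROC FREQ code, replace CORRECT in the BINOMIAL and RISKDIFF options with the matching CL= choice. SAP 6.2.2 needs no change. If the SAP is already final, its introduction provides for later changes to be documented in the clinical study report.

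The cost is a few words and two code options, with no new data, endpoints or visits. Intervals at or near no responders become visibly wider, which is the honest result. Mid-range differences become shorter: at 60% v 38.6%, the mean width falls from 0.71 to 0.56 with Newcombe.

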8.5.2. Secondary Analyses

8.5.2.1. Estimand

The main estimand corresponding to the treatment policy strategy for the key secondary endpoints is defined with the same attributes as in the primary estimand except that the variable / endpoint and population-level summary are endpoint specific. The key secondary endpoints are listed in Section 3.1.2. For the binary endpoints, the population-level summary is the treatment difference in the percentage of subjects meeting specified criteria for response between each filgotinib group and the placebo group. For the continuous endpoints, the population-level summary is the mean treatment difference between each filgotinib group and the placebo group.

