- Step 2: Within each analysis visit window, select the component-level data based on the rules for selecting efficacy data as above
- Step 3: Calculate the composite endpoint based on the selected component-level data in Step 2.

Missing Data Consideration

Unless specified otherwise, below are the consideration for the missing data that will be used throughout the efficacy analyses:

Observed case (OC): Missing values remain missing. For the categorical composite endpoints, in the case that some components are missing, the composite endpoint assessment will be derived based on the nonmissing components. If nonmissing components are not sufficient to determine final composite endpoint, then the composite endpoint will be set as missing. For continuous composite endpoints, if any components are missing, the composite endpoints will be set as missing.

If a subject only has baseline measurements, OC analyses will not include this subject.

For subjects who were re-randomized, the baseline value for the LTE phase will be the last nonmissing measurement obtained on or prior to the first dose date of filgotinib in the LTE. The change from baseline at analyses visits during LTE phase will be assessed from the re-randomized baseline of the LTE phase. The evaluation of response at analysis visits during LTE phase will be assessed from the re-randomized baseline of the LTE phase.

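### ACR50, PASI75 and MDA are analysed on observed cases, which does not match their FAS treatment-policy estimand; ACR20 at the same Week 12 visit as ACR50 is multiply imputed (minor)

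*SAP*

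**What the plan says.** **Estimand.** SAP 6.1 states: "Treatment policy estimand is defined for the primary and key secondary as well as other secondary efficacy endpoints". Its first attribute is "Population: Subjects in the FAS". Protocol 8.5.2.1 says that the key secondary estimand "is defined with the same attributes as in the primary estimand", apart from the variable and the summary measure.

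**Binary key secondary endpoints.** For ACR50, PASI75 and MDA, SAP 6.3.2 says that "the observed response rate and 2-sided 95% CI based on normal approximation with continuity correction will be provided by visit". It adds an unstratified rate difference with a CI of the same type, and a p-value from the 6.2.2 logistic model "with observed cases for testing the superiority of filgotinib 200 mg or filgotinib 100 mg as compared to placebo". SAP 6.1 defines the term: "Observed case (OC): Missing values remain missing". It also says: "If a subject only has baseline measurements, OC analyses will not include this subject".

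**ACR20.** SAP 6.2.2 imputes missing Week 12 ACR20 by MI under MAR. There are 20 imputed datasets, treatment and strata are covariates, and post-baseline data up to Week 16 enter a longitudinal model. SAP 6.3.2 uses the same MI for the ACR20 non-inferiority test.

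**Continuous key secondary endpoints.** These use an MMRM, with descriptive statistics if the data are too few.

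**Status of the results.** SAP 1.3 reports that the sponsor terminated the study after 67 subjects were enrolled. SAP 3.4 and 6.1 make all p-values nominal, and SAP 6.5 plans no sensitivity analyses.

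**The concern.** The estimand covers every FAS subject. The estimator covers only those whose outcome can be determined at the visit, and the SAP gives no assumption that links the two. The contrast is sharpest at Week 12. A subject without enough ACR components there is kept for ACR20 through imputation but may drop out of the ACR50 analysis, so the two response rates can rest on different subjects.

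The observed-case logistic model adjusts only for treatment and strata, and the reported rates and differences are unadjusted. Neither uses the subject's earlier visits. If subjects who had not responded earlier are more often missing, those who remain over-represent responders. The rates are then too high, and the difference moves in a direction that depends on which arm loses more non-responders. With no sensitivity analysis, nothing in the output would show this.

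**Working it through.** **1. Passages side by side**

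| Endpoint | Visit | Estimand population | Missing outcome |
|---|---|---|---|
| ACR20 v placebo (6.2.2) | Week 12 | FAS | MI under MAR |
| ACR20 non-inferiority (6.3.2) | Week 12 | FAS | MI under MAR |
| ACR50 (6.3.2) | Week 12 | FAS | left missing |
| PASI75, MDA (6.3.2) | Week 16 | FAS (PASI75: BSA ≥3% subset) | left missing |
| HAQ-DI, PCS, LEI, FACIT-Fatigue, LDI (6.3.2) | Week 12 or 16 | FAS (LEI, LDI: subsets) | MMRM on all visits |

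Among the key secondary endpoints, the binary ones alone are planned as observed-case at a single visit.

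**2. Possible size of the bias**

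The documents give no dropout rate and no expected ACR50, PASI75 or MDA rate, so there is no plan figure to reproduce. Everything below is assumed for illustration:

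- Week 12 ACR50: 15% placebo, 35% filgotinib (true difference 20 points).
- Week 8 ACR50: 12% and 30%; latent normal correlation between visits 0.75.
- Missingness at Week 12 depends only on Week 8 status: 5% in Week 8 responders, 15% to 40% in non-responders.

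Let p be the Week 8 response rate, r1 and r0 the Week 12 response rates in Week 8 responders and non-responders, and m1 and m0 their missing fractions.

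- FAS rate = p·r1 + (1−p)·r0
- Observed-case rate = [p(1−m1)r1 + (1−p)(1−m0)r0] / [p(1−m1) + (1−p)(1−m0)]

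The bivariate normal gives r1 = 0.609 and r0 = 0.087 on placebo, and 0.733 and 0.186 on filgotinib. As a check, 0.12×0.609 + 0.88×0.087 = 0.15 and 0.30×0.733 + 0.70×0.186 = 0.35.

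First row of the table below:

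- Placebo: (0.12×0.95×0.609 + 0.88×0.60×0.087) / (0.114 + 0.528) = 0.1156/0.642 = 18.0%.
- Filgotinib: (0.30×0.95×0.733 + 0.70×0.85×0.186) / (0.285 + 0.595) = 0.3195/0.880 = 36.3%.
- Difference: 18.3 points.

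| Non-responder dropout, placebo / filgotinib | Missing overall | Observed-case rates | Difference (true 20) |
|---|---|---|---|
| 40% / 15% | 35.8% / 12.0% | 18.0% v 36.3% | 18.3 |
| 15% / 15% | 13.8% / 12.0% | 15.6% v 36.3% | 20.7 |
| 30% / 30% | 27.0% / 22.5% | 16.9% v 38.7% | 21.8 |
| 40% / 40% | 35.8% / 29.5% | 18.0% v 40.7% | 22.7 |
| 15% / 40% | 13.8% / 29.5% | 15.6% v 40.7% | 25.1 |

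An estimator that uses Week 8 status returns 20 in every row. That follows from the assumption, because missingness was made to depend on Week 8 status alone. If missingness is unrelated to response, observed case is unbiased as well.

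**3. Comparison with sampling error**

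At 2:2:1:2, 67 subjects give 67×2/7 ≈ 19 in each filgotinib arm and in placebo. With 15% v 35% and nobody missing, SE = √(0.15×0.85/19 + 0.35×0.65/19) = 13.7 points. The planned continuity-corrected CI has half-width 1.96×13.7 + ½(1/19 + 1/19)×100 = 26.8 + 5.3 ≈ 32 points. The bias range of −1.7 to +5.1 points is at most 5.1/13.7 = 0.37 SE.

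**4. What the missing count alone allows**

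If a fraction m is missing in each arm, the FAS difference lies within (1−m)×(observed-case difference) ± m. For an observed difference of 20 points, 10% missing gives 18 ± 10, or 8 to 28. With 30% missing it is 14 ± 30, or −16 to 44. A reader needs the numbers missing by arm to judge which applies.

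**The case against.** Several points on the other side stand.

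- **No protocol rule is broken.** A reader might infer that the SAP departs from the protocol and that SAP 6.5 fails to list the change. The documents do not support this. Protocol 8.5.1.2 specifies MI for the primary estimator only. Protocol 8.5.2.2.1 gives logistic regression for binary key secondary endpoints with no missing-data rule, and Protocol 8.5 leaves further detail to the SAP.
- **This is not a completer analysis.** A reader might take observed case to mean subjects who finished treatment. SAP 6.1 keeps data after study drug discontinuation through Week 16, and composites with missing components are still classified when the remaining components suffice. A subject who leaves after Week 12 still counts for ACR50.
- **The same-visit contrast applies only to ACR50.** PASI75 and MDA are Week 16 endpoints, and SAP 6.4.2 analyses ACR20 outside Week 12 on observed outcomes too.
- **The dropout mechanism is assumed.** Protocol 3.2 and 6.1.3 ask subjects who stop drug to continue assessments to Week 16, which limits loss driven by poor response. Documented causes of lost data include sponsor termination (SAP 1.3) and COVID-19 disruption (SAP 4.4). If these are unrelated to response, observed case is unbiased.
- **Non-responder imputation could do more harm.** With 30% missing for administrative reasons in both arms, observed case stays at 20 points, while counting the missing as failures gives 0.7×35 − 0.7×15 = 14.
- **MI may be unstable.** A 15% rate in 19 subjects is about 3 responders, and PASI75 uses only a subset. The SAP itself expects that the logistic model may not be usable.

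These points limit the size of the problem and shape the remedy. They do not explain why two endpoints from the same components at the same visit are handled differently. If MI is acceptable for ACR20 in these 67 subjects, sparse data are no general reason to withhold it from ACR50.

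**Conclusion.** The mismatch is real. SAP 6.1 and Protocol 8.5.2.1 set a FAS treatment-policy estimand for ACR50, PASI75 and MDA, and SAP 6.3.2 leaves out FAS subjects without a determinable outcome, without stating an assumption. At Week 12 it also separates ACR50 from ACR20 with no reason given.

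Under the assumed scenarios, a true 20-point difference is reported as about 18 to 25 points. These figures rest on assumed response rates, an assumed correlation and dropout tied to Week 8 status; the documents neither support nor exclude them. A reader might infer that the key secondary results will be materially wrong. That does not follow, because the bias is under 0.4 SE at about 19 per arm, all p-values are nominal, and the graphical testing procedure has been dropped (SAP 6.5). The point is minor.

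**What to change.** - Apply the SAP 6.2.2 MI model to ACR50 at Week 12, and to MDA and PASI75 at Week 16 where the imputation model can be fitted. Take the p-value, rate difference and CI from the imputed data, and keep observed cases as the supporting display.
- Where MI cannot be fitted, keep observed cases, state that they do not estimate the FAS estimand, and report the number missing by arm and visit.
- Do not fall back to non-responder imputation, which would count subjects lost to sponsor termination as failures.

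The cost is a few lines in SAP 6.3.2 and re-use of the ACR20 imputation program. The downside is some model dependence when responses are sparse, most likely for PASI75.
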